# 10.3 Reporting of Protocol Deviations

Analysis set: SAF

Please see Section 8.1 for details on the definition and collection of protocol deviations.

The following summary tables and listings of protocol deviations will be provided:

- Frequency table by reason of IPDs
- Frequency table of IPDs attributed to the impact of the COVID-19 pandemic
- Listing of IPDs

CONFIDENTIAL

 Listing of protocol deviations attributed to the impact of COVID-19, including severity level of the deviation (important vs. non-important)

#### 11 Demographics and Other Baseline Characteristics

#### 11.1 Demographics

Analysis set: SAF

Demographic characteristics will be listed and summarized by dose level and overall as follows:

- Demographic characteristics
  - Gender: male, female
  - Race: White, Black or African American, Asian, American Indian or Alaska Native, Native Hawaiian or Other Pacific Islander, Not collected at this site, other
  - Ethnicity: Hispanic or Latino, Not Hispanic or Latino
  - Age (years)
  - Age categories:
  - < 65 years, ≥ 65 years

  - 65-74, 75-84, ≥85
- Eastern Cooperative Oncology Group Performance Status (ECOG PS)
- Physical measurements
  - Height (cm)
  - Weight (kg)
  - BMI (kg/m²)

Specifications for computation:

- Age [years]
  - (date of given informed consent date of birth + 1) / 365.25
  - In case of missing day for at least one date, but month and year available for both dates. the day of informed consent and the day of birth will be set to 1 and the formula above will be used.
  - In case of missing month for at least one date, but year available for both dates, the day and the month of informed consent and the day and month of birth will be set to 1 and the formula above will be used.
- Site codes will be used for the determination of the participant's pooled region.

BMI (kg/m²) = weight (kg) / [height (cm) x height (cm)] x 10000

A listing showing the relevant demographic data will also be produced.

### 11.2 Medical History

Analysis set: SAF

The medical history will be summarized from the "Medical History Details" eCRF pages, using the latest version of Medical Dictionary for Regulatory Activities (MedDRA), preferred term (PT) as event category and MedDRA system organ class (SOC) body term as body system category.

Medical history will be displayed in terms of frequency tables: ordered by primary SOC and PT in alphabetical order.

A supportive listing of medical history data by participant will include all the relevant data fields as collected on the "Medical History" eCRF page.

#### 11.3 Other Baseline Characteristics

[figure not shown]
#### Disease Characteristics

Analysis set: SAF

Information regarding disease characteristics collected on the "Disease History" CRF page will be summarized and listed as follows:

- Type of cancer: Breast cancer, serous epithelial ovary cancer, bladder cancer, colon cancer, non-small cell lung cancer, castration resistant prostate cancer, stomach cancer, uterine cancer, melanoma, small cell lung cancer, rectal cancer, prostate cancer, other cancers
- Tumor histopathologic/ cytologic grade: GX: Grade cannot be assessed (undetermined grade),
   G1: Well differentiated (low grade), G2: Moderately differentiated (intermediate grade), G3:
   Poorly differentiated (high grade), G4: Undifferentiated (high grade)
- Time since initial cancer diagnosis (months), defined as (date of first study treatment date of initial diagnosis)/30.4375
- Time since documented locally advanced, inoperable, or metastatic disease diagnosis (months), defined as (date of first study treatment – date of documented locally advanced, inoperable, or metastatic disease diagnosis)/30.4375
- Stage at initial diagnosis
- Stage at study entry
- TNM classification at initial diagnosis
- TNM classification at study entry

Site of primary tumor and subsites will be presented in a listing.

#### 12 Previous or Concomitant Medications/Procedures

Analysis set: SAF

#### 12.1 Prior Anti-Cancer Treatments

The prior anti-cancer treatments and procedures are collected from the "Prior Anti-cancer Surgeries Details", "Prior Anti-cancer Drug Therapies Details", and "Prior Anti-cancer Radiotherapy Details" eCRF pages.

The number and percentage of subjects in each of the following anti-cancer therapy categories will be tabulated:

- Subjects with at least one type of prior anti-cancer treatment
- Subjects with at least one prior anti-cancer drug therapy
- Subjects with at least one prior anti-cancer radiotherapy
- Subjects with at least one prior anti-cancer surgery
- Type of prior anti-cancer drug therapy: Cytotoxic therapy / Endocrine therapy / Monoclonal antibody therapy / Small molecules / Immunotherapy / Other
- Intent of Therapy: Neoadjuvant / Adjuvant / Metastatic or Locally advanced
- For Metastatic/ Locally advanced intent, number of therapy lines: 1/2/3/≥4
- Best response: Complete Response (CR) / Partial Response (PR) / Stable Disease (SD) / Non-CR/Non-PD / Progressive Disease (PD) / Not Evaluable (NE) / Unknown. Best response is derived from the last treatment regimen.

The prior anti-cancer drugs will also be extensively detailed with the number and percentage of subjects by the drug class and PT in a separate table. A subject will be counted only once within a given drug class and within a given drug name, even if the subject received the same medication at different times. The summary tables will be sorted on decreasing frequency of drug class and decreasing frequency of drug name in a given drug class, based on the incidence in the "Overall" column. In case of equal frequency, alphabetical order will be used.

The listings of prior anti-cancer treatments and procedures will also be provided:

- listing of prior anti-cancer drug therapies
- listing of prior anti-cancer radiotherapy
- listing of prior anti-cancer surgeries

These will include dose level, subject identifier, and all the relevant collected data fields on the corresponding eCRF pages (ordered by dose level, subject identifier and therapy start date).

#### 12.1 Previous and Concomitant Medications/Procedures

Previous and concomitant medications are collected on the "Relevant Previous Medications Details" and "Concomitant Medications Details" eCRF pages. Prior and concomitant procedures are collected on the "Concomitant procedures details" eCRF page.

Previous medications are medications, other than study medications and pre-medications for study intervention, which are started before first administration of any study intervention.

Concomitant medications are medications, other than study medications and pre-medications for study intervention, which started prior to first dose date of study intervention and continued during the on-treatment period as well as those started during the on-treatment period.

Previous medications and concomitant medications will be summarized separately showing the number of subjects and percentage of subjects having taken a given drug, summarized by Anatomical Therapeutic Chemical classification class (ATC-2nd level) and PT, displayed by dose level and overall. ATC and PT will be summarized as given from the World Health Organization (WHO) dictionary current version. In case multiple ATCs are assigned to a drug, all ATC-2nd level will be used for reporting. In case the date values will not allow for unequivocal classification of a medication as concomitant, the medication will be considered as a concomitant medication.

A subject will be counted only once within a given drug class and within a given drug name, even if the subject received the same medication at different times or multiple medications within a given drug class.

The summary tables will be sorted on decreasing frequency of drug class and decreasing frequency of drug name in a given drug class, based on the incidence in the "Overall" column. In case of equal frequency regarding drug class (respectively drug name), alphabetical order will be used.

Previous and concomitant medication data will be listed separately. The following variables will be included in the listings: cohort dose level, subject identifier, and all corresponding collected data fields on the corresponding eCRF pages. The listings will be sorted by cohort dose level, subject identifier, and the start date of the medication.

Prior and concomitant procedures data collected on the "Prior Anti-cancer Surgeries Details" and "Concomitant Procedures Details" eCRF pages will be listed. Cohort dose level, subject identifier, and all collected data fields on the corresponding eCRF pages will be included in the listings. The listings will be sorted by cohort dose level, subject identifier, and the start date of the procedure.

Premedication data (reported on the "Premedication Details" eCRF page) given before each study intervention administration will be listed.

# 12.2 Subsequent Anti-Cancer Therapies/Procedures

The number of subjects who received treatment after discontinuation will be summarized as reported on the "Anti-cancer Treatment after Discontinuation Details", "Radiotherapy after Discontinuation Details" and "Surgery after Discontinuation Details" eCRF pages.

CONFIDENTIAL

The number and percentage of subjects in each of the following anti-cancer therapy categories will be tabulated:

- Subjects with at least one type of subsequent anti-cancer treatment
- Subjects with at least one subsequent anti-cancer drug therapy
- Subjects with at least one subsequent anti-cancer radiotherapy
- Subjects with at least one subsequent anti-cancer surgery
- Type of subsequent anti-cancer therapy: Cytotoxic therapy / Endocrine therapy / Monoclonal antibody therapy / Small molecules / Immunotherapy / Other
- Best response: Complete Response (CR) / Partial Response (PR) / Stable Disease (SD) / Non-CR/Non-PD / Progressive Disease (PD) / Not Evaluable / Unknown. Best response is derived from the last treatment regimen.

Anti-cancer treatment after discontinuation will be provided in a listing with data retrieved from "Anti-Cancer Treatment after Discontinuation Details", "Radiotherapy after Discontinuation Details" and "Surgery after Discontinuation Details" eCRF pages.

# 13 Study intervention Compliance and Exposure

Analysis set: SAF

All dosing calculations and summaries, as well as the listings of study drug administration, will be based on the "M3814 Administration Details", "M3814 Accountability" "Avelumab Administration Details," "Radiotherapy Administration" "M3814 Termination", "Avelumab Termination" and "Radiotherapy Termination" eCRF pages.

- Part A and Part FE: M3814 will be administered twice daily, without interruption, in combination with avelumab, administered once every two weeks, starting on Day 1 until PD or unacceptable toxicity.
- Part B: M3814 will be administered once a day. RT will be given at the dose of 3 Gy per day. M3814 and RT will both be given starting Day 1 for 5 days/week for 2 weeks, at which point, both M3814 and RT are discontinued. Avelumab will be administered once every two weeks starting on Day 1 until PD or unacceptable toxicity.

### Duration of therapy

Study intervention duration will be calculated based on the number of planned administration days expected for each treatment component. Duration of therapy is defined as follows:

Parts A and FE:

Duration of avelumab (weeks) = 
$$\left( \frac{\text{date of last dose-date of first dose} + 14}{7} \right)$$
Duration of M3814 (weeks) = 
$$\left( \frac{\text{date of last dose-date of first dose} + 1}{7} \right)$$

#### Part B:

Duration of therapy will be summarized on a table with summary statistics for each treatment by cohort dose level. Details will also be included in a listing.

#### Cumulative dose

The overall cumulative dose per subject across all cycles is the sum of actual doses the subject received (i.e., total dose administered).

Cumulative dose is measured in mg for avelumab and M3814 and Gy for radiotherapy.

Cumulative actual dose will be summarized on a table with summary statistics for each treatment, by cohort dose level. Details will also be included in a listing.

## Dose Intensity

Each cycle is defined by a 2-week period. M3814 will be administered once a day for 5 days followed by 2 days off for 10 days in total (i.e., on the same schedule as the RT). Avelumab will be administered Q2W as an IV infusion over 1 hour, starting on Day 1, at a fixed dose of 800 mg in all dose levels.

The dose intensity will be calculated for each subject across all cycles.

Dose intensity is defined for avelumab (mg/cycle), M3814 (mg/cycle), and RT (Gy/cycle) as follows:

Dose Intensity = 
$$\frac{\text{actual cumulative dose}}{\frac{\text{duration of therapy (weeks)}}{2 \text{ weeks/cycle}}}$$

Dose intensity will be summarized on a table with summary statistics for each treatment, by cohort dose level. Details will also be included in a listing.

### Relative Dose Intensity

The relative dose intensity is defined as the actual dose intensity divided by the per-protocol planned dose level per cycle and is expressed as a percentage.

Relative Dose Intensity = 
$$\left(\frac{\text{Dose Intensity}}{\text{planned dose level per cycle}}\right)$$

Relative dose intensity for each treatment will be included in a listing and will be summarized in the following categories, by cohort dose level:

- 0 <50%
- o 50% to < 80%
- o 80% to < 90%
- o 90% to 110%
- 0 > 110%

#### Dose Reductions

For avelumab, a dose reduction is defined as an actual non-zero dose < 90% of the per-protocol dose within a given cycle.

For M3814, a dose reduction is defined as an actual non-zero cumulative dose < 90% of the planned (per-protocol) cumulative dose for a given treatment cycle (i.e., two-week period). Any skipped doses within the cycle will contribute to the calculation of the dose reduction (i.e., will be included in the denominator of the calculation). If a subject permanently discontinues treatment before completing a full cycle, the planned cumulative dose will be calculated as planned cumulative dose expected between the first dose of treatment on the cycle and the last.

Dose reductions are counted on a per-cycle basis and do not consider whether previous doses were reduced.

Number and percentage of subjects with at least one dose reduction, as well as a breakdown of cycles with dose reductions  $(1/2/3/\ge4)$  will be summarized by cohort dose level.

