6.6.1 Dose Selection (Part A and Part B)

Part A:

- The starting dose of M3814 will be 100 mg BID. Subsequent doses and schedules will be determined by the SMC (see Section 4.3.1 for dose rationale).
- Avelumab will be administered Q2W as an IV infusion over 1 hour, starting on Day 1, at a fixed dose of 800 mg in all dose levels. Guidance on premedication is given in Section 6.5.5.

Part B:

- The starting dose of M3814 in the first cohort of participants will be 100 mg total daily dose
 (i.e. 2-fold lower than in Part A). However, this starting dose might be adjusted by the SMC
 based on safety, PK and Pd data generated during the first dose level in Part A and/or emerging
 data from the ongoing clinical studies involving M3814.
- Avelumab will be administered Q2W as an IV infusion over 1 hour, starting on Day 1, at a fixed dose of 800 mg in all dose levels. Guidance on premedication is given in Section 6.5.5.
- Radiotherapy: 3 Gy per fraction per day for 5 days a week to a total dose of 30 Gy, starting on Day 1 with M3814.

The SMC will review the safety and any available PK/Pd data on a regular basis. During Part A and Part B, the SMC will decide on relevant DLTs (Section 6.6.3) based on protocol criteria. They will decide by consensus on dose escalation or de-escalation of M3814, or suspension of enrollment and/or declaration of the maximum safe dose (i.e. maximum administered dose/MTD) and the RP2D of M3814 in combination with avelumab (Part A) and with avelumab and RT (Part B).

For Part A only, in the event that an AE which meets the definition of DLTs as defined per the protocol occur in Part FE, after a higher dose level has been opened in Part A, the data will be reviewed by the Sponsor and the SMC to determine the best course of actions for currently enrolling participants at the highest dose level.

The DLT period is considered completed, and a participant evaluable for dose escalation decisions, when the minimum safety evaluations have been performed (hematology, chemistry, and clinical assessments), and the participant has received:

- Part A: at least 80% of the planned doses of M3814 (i.e. 34 of 42 doses with BID dosing regimen) and 100% of the planned avelumab doses (2 administrations) during the DLT assessment period of 3 weeks.

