6.9 Management of Adverse Events of Interest

6.9.1 Adverse Drug Reactions Requiring M3814 Treatment Discontinuation or Modifications

Part A and Part FE (M3814 + Avelumab)

There is no dose reduction allowed for M3814 or avelumab during the DLT period or the FE Assessment Period. The study intervention can only be discontinued due to toxicity. Details on criteria for discontinuation of study interventions are in Section 7.1.

After the DLT and the FE Assessment Period, if not tolerated, treatment with M3814 may be interrupted, modified or stopped at the Investigator's discretion.

Where a SAE (Grade \geq 3) is believed to be due to M3814, M3814 will be withheld until the SAE has resolved to Grade \leq 2. On subsequent cases of the same SAE, permanent dose reductions in 50 mg steps must be done.

In case of a nonserious AE Grade 3, assessed by Investigators as related to M3814, a dose reduction should be considered.

In the case of participants vomits within 1 hour of M3814 dose, please see Section 6.6.5.4.

If M3814 50 mg BID is not tolerated, M3814 will be stopped. Any change from dosing schedule, dose interruptions, or dose reductions should be recorded in the eCRF.

If avelumab treatment is discontinued while M3814 treatment is ongoing, M3814 treatment could be continued if the Investigator believes the participant is experiencing clinical benefit from M3814 treatment.

Part B (M3814 + Radiotherapy + Avelumab)

The formal criteria for M3814 and RT dose modification are presented in Table 15.

Early and late toxicities related to RT and/or M3814 will be managed according to the local institute's guidelines.

Table 15 Dose Modifications for M3814 and Radiotherapy During Part B of the Study

Toxicity	Dose Modifications ^a		
	M3814 ^b	Radiotherapy ^c	
Toxicities in Radiation Field Grade ≥ 3 • Mucositis • Radiation dermatitis	Temporarily interrupt treatment. Resume treatment once severity resolves to Grade ≤ 2	Temporarily interrupt treatment. Resume treatment once severity resolves to Grade ≤ 2	
 Systemic Toxicities Hematologic Toxicities: Any Grade ≥ 4 toxicity, excluding: Grade 4 neutropenia lasting for ≤ 5 days and not associated with fever Isolated Grade 4 lymphocytopenia without clinical correlate 	Temporarily interrupt treatment. Resume treatment (at the same dose) once severity resolves to Grade ≤ 1 or Baseline. In case of a second recurrence, permanently discontinue study intervention.	No action to be taken.	

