Adverse events observed from the first dose until 30 days after last study intervention administration (i.e. TEAEs) will be summarized according to MedDRA system organ classes and preferred terms. The incidence and type of the following will be analyzed:

- TEAEs and SAEs
- TEAEs and SAEs related to study intervention
- TEAEs with NCI-CTCAE Grades ≥ 3
- TEAEs related to study intervention with NCI-CTCAE Grades ≥ 3
- AEs leading to withdrawal, dose modifications, or permanent study intervention discontinuation
- Deaths.

Participants who terminate treatment will be displayed in a by-participant listing and summarized by primary withdrawal reason.

All reported deaths after first dose of study intervention as well as reasons for death will be tabulated (for all participants enrolled). Deaths within 30 days from last dose administration and deaths beyond this period up to 90 days follow-up and reasons for them will also be tabulated.

Laboratory Variables

Laboratory results will be classified by grade according to NCI-CTCAE v 5.0. The worst on-study grades after the first study intervention will be summarized.

Shifts in toxicity grades from first treatment to highest grade will be displayed. Results for variables that are not part of NCI-CTCAE will be presented as below, within, or above normal limits. Only participants with postbaseline laboratory values will be included in these analyses.

Physical Examination

Physical examination, including vital signs (body temperature, respiratory rate, heart rate, and blood pressure), and 12-lead ECG, recorded at Baseline and after administration of study intervention will be presented.

Further details will be provided in the Integrated Analysis Plan.

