### Therapy Interruptions

A therapy interruption is defined as omission of a full cycle of a planned study intervention. Therapy interruptions are only defined if the intervention is later restarted.

Avelumab: A therapy delay of greater than 13 days is considered a therapy interruption.

M3814 (Parts A and FE only): fourteen consecutive days of missed M3814 is considered a therapy interruption.

The number and percentage of subjects with an interruption in study drug administration and the longest observed interruption (cycles) per subject will be summarized by cohort dose level. If possible, the number and percentage of subjects with therapy interruptions attributable to the COVID-19 pandemic will also be presented.

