# 15.1.2 Adverse Events Leading to Study Intervention Discontinuation

An overall summary table of AEs leading to permanent study intervention discontinuation will be prepared and will tabulate the number and percentage of participants with AEs in the following categories:

- Any TEAE leading to permanent discontinuation of at least one study intervention
- TEAEs leading to permanent discontinuation of M3814
- TEAEs leading to permanent discontinuation of avelumab
- TEAEs leading to permanent discontinuation of RT (Part B only)
- TEAEs leading to permanent discontinuation of both M3814 and avelumab
- TEAEs related to M3814 leading to its permanent discontinuation
- TEAEs related to avelumab leading to its permanent discontinuation
- TEAE related to both leading to permanent discontinuation
- TEAEs related to RT leading to its permanent discontinuation
- AESIs leading to permanent discontinuation of avelumab, by category

In addition, tables summarizing the frequency of subjects with TEAEs, presented by SOC and PT, in the following categories will be prepared.

- TEAEs leading permanent discontinuation of avelumab
- TEAEs leading permanent discontinuation of M3814
- TEAEs leading permanent discontinuation of RT (Part B only)
- TEAEs leading permanent discontinuation of M3814 and avelumab
- TEAEs related to avelumab leading to its permanent discontinuation
- TEAEs related to M3814 leading to its permanent discontinuation

As action taken with study intervention will be detailed in the full listing of AEs, no separate listing of AEs leading to permanent discontinuation of study intervention will be produced.

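### The SAP drops the protocol's analysis of adverse events leading to dose modification, and its M3814 reduction and interruption rules do not match the protocol's terms

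*SAP*

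**What the plan says.** **Protocol.** Section 6.9.1 gives two separate M3814 actions in Parts A and FE. For a Grade 3 or higher SAE attributed to M3814, the drug is withheld until the event falls to Grade 2 or below, with no minimum length of hold. Then: "On subsequent cases of the same SAE, permanent dose reductions in 50 mg steps must be done". No M3814 reduction is allowed in the DLT or food-effect assessment period. Reductions and interruptions are both to be recorded in the eCRF. In Part B, Table 15 makes temporary interruption the main M3814 action. Section 9.4.2 lists, among the items whose incidence and type will be analysed, "AEs leading to withdrawal, dose modifications, or permanent study intervention discontinuation".

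**SAP.** For M3814, section 13 states that "a dose reduction is defined as an actual non-zero cumulative dose < 90% of the planned (per-protocol) cumulative dose for a given treatment cycle" and that "Any skipped doses within the cycle will contribute to the calculation of the dose reduction". On cycle length: "Each cycle is defined by a 2-week period". For Parts A and FE only, and only if treatment restarts, "fourteen consecutive days of missed M3814 is considered a therapy interruption". Therapy delays are defined for avelumab alone. No reduction, delay or interruption is defined for RT. Section 15.1.2 has rows such as "TEAEs leading to permanent discontinuation of M3814", all for permanent discontinuation, and leaves other actions taken to the AE listing. Section 15.1.1 has no table by action taken. Section 7 declares only changes to PK parameters.

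**The concern.** Two things go wrong. First, an analysis named in the protocol has no table in the SAP, and its removal is not declared. Second, the SAP uses the protocol's words for different things. Its reduction is a shortfall in total milligrams over two weeks, whatever the cause. Its interruption is a whole missed cycle. A hold for toxicity, a few forgotten doses and a lowered dose level can all fall under one label, and some lowered dose levels fall under none.

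M3814 in Parts A and FE is given until progression or unacceptable toxicity, while the Part A DLT window is 3 weeks. How often participants need a hold or a lower dose is therefore useful longer-term tolerability information in the CSR. The tables as specified cannot be read that way.

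**Working it through.** **Inputs.** Cycle of 14 days (SAP 13, Dose Intensity); BID dosing in Parts A and FE; strict cut below 90% (SAP 13, Dose Reductions); 50 mg step (Protocol 6.9.1); example Part A levels 50, 100, 200, 400 and 800 mg BID (Protocol Table 13).

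**Dose count.** Protocol 6.6.1 requires "at least 80% of the planned doses of M3814 (i.e. 34 of 42 doses with BID dosing regimen" in 3 weeks. Check: 2 × 21 = 42; 0.80 × 42 = 33.6, rounded up to 34. This reproduces. The same rate gives 2 × 14 = 28 doses per cycle. That is an assumption, because the SAP's cycle text describes only the 10-dose Part B schedule.

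**Missed doses at an unchanged dose level**, (28 − k)/28:

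| Missed doses k | % of plan | Counted as reduction |
|---|---|---|
| 1 | 96.4 | no |
| 2 | 92.9 | no |
| 3 | 89.3 | yes |

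- *DLT period.* An evaluable participant may miss 42 − 34 = 8 doses. Three of these in one cycle produce a reported reduction in a period when the protocol allows none.
- *Protocol-required hold.* Protocol 6.5.4 stops M3814 at least 24 h before and 24 h after palliative RT. With 12-hourly dosing, a 48 h gap between doses omits the doses at 12, 24 and 36 h. That is at least 3 doses, and a reduction if they fall in one cycle.
- *Illustration.* If doses were missed independently with probability 2%, 5% or 10% (assumed values), the chance of 3 or more misses in 28 would be 1.8%, 16.3% or 54.1% per cycle, with no toxicity at all.

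**Full-day holds** (h days, any position relative to cycle boundaries):

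| Hold | Interruption | Cycles counted as reductions |
|---|---|---|
| 1 day | no | 0 |
| 2 days | no | 0 or 1 |
| 3 to 13 days | no | 1 or 2 |
| 14 days | yes | 0, 1 or 2 |

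**One sustained 50 mg step.** The protocol does not say whether the step is per dose or per day. Per dose, the fraction left is (d − 50)/d; per day it is (2d − 50)/(2d), where d is the mg per BID dose.

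| Level (BID) | Per dose | Counted | Per day | Counted |
|---|---|---|---|---|
| 100 mg | 50.0% | yes | 75.0% | yes |
| 200 mg | 75.0% | yes | 87.5% | yes |
| 400 mg | 87.5% | yes | 93.75% | no |
| 500 mg (not in Table 13) | 90.0% | no | 95.0% | no |
| 800 mg | 93.75% | no | 96.9% | no |

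Per dose, the step is missed from 500 mg BID upward. Per day, it is missed when 50/(2d) ≤ 0.10, that is from 250 mg BID, which among the example levels means 400 and 800. A step starting mid-cycle can also be missed in that cycle. At 400 mg BID (per dose), 12 of 14 days at 350 mg are needed: (5600 − 600)/5600 = 89.3%, against (5600 − 550)/5600 = 90.2% for 11 days.

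**Part B** (10 planned doses): 1 missed leaves 90.0%, not counted; 2 missed leave 80.0%, counted as a reduction. No M3814 hold can be an interruption, because that category excludes Part B.

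**The case against.** The best defence is that SAP 13 is a compliance and exposure section. It states its metric openly, says that skipped doses count, and does not claim to measure toxicity. Treating an interruption as omission of a full cycle is internally consistent. No data are lost: duration, cumulative dose, dose intensity and relative dose intensity are summarised, and dosing and AE actions taken are listed. The study is exploratory with 3 to 6 participants per level, so the listings can be read person by person. The reduction mandated after a recurrent SAE also follows an earlier hold. If that hold cost 3 or more doses in a cycle, the participant is already counted.

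Much of this stands, and it limits the consequence to labelling and to a missing table. It does not remove the point. A listing is not the incidence analysis that Protocol 9.4.2 names. Relative dose intensity carries no reason, and a step leaving 93.75% sits in its 90% to 110% band. The earlier-hold argument does not cover cycle counts or discretionary reductions.

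A reader might infer that three missed tablets make a reduction. With 50 mg tablets that is true only at 50 mg BID (25 of 28). At 100 mg BID it takes 6 of 56 tablets, and at 800 mg BID 45 of 448. A reader might also infer that true reductions are missed in general. At 100, 200 and 400 mg BID a sustained per-dose step is counted, as are two steps at 800 mg BID (700/800 = 87.5%).

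**Conclusion.** The point holds as a reporting defect. An analysis of AEs leading to dose modifications, named in Protocol 9.4.2, has no SAP table and no declared removal. This depends on no threshold or dose level. Separately, the SAP 13 rules misclassify the protocol's two M3814 actions:

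- 3 missed doses in a BID cycle count as a reduction.
- Full-day holds of 3 to 13 days are never interruptions and appear as reductions.
- Part B holds have no interruption category.
- A single 50 mg step goes uncounted at 500 mg BID or above if it is per dose, and at the 400 and 800 mg BID example levels if it is per day.

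The CSR modification tables would therefore mix non-adherence, protocol-required holds, toxicity holds and true reductions.

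The figures rest on 28 planned doses per cycle and on full-day holds. The 800 mg BID figure matters only if that example level is reached.

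It is tempting to conclude that the tolerability of the RP2D is misreported. The documents do not support that. The SMC sets the RP2D from DLT, safety and PK/Pd data (Protocol 6.6.1; SAP 6), using outputs specified in its own charter (SAP 4). The SAP's interim safety analysis follows RP2D selection (SAP 6.1). Nothing makes this table an input to that decision.

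**What to change.** 1. **SAP 15.1.2:** add tables of TEAEs leading to dose reduction or interruption of M3814 and of RT, and to interruption or delay of avelumab, from the action-taken field. If the sponsor does not want them, declare the omission in SAP 7.
2. **SAP 13:** reconcile the terms with Protocol 6.9.1. Count an M3814 reduction as a recorded dose below the assigned level, and an interruption as any recorded hold, including in Part B. Report duration and, where collected, the reason. Keep less than 90% of planned dose only as a dose-intensity category. State the planned number of M3814 doses per cycle for Parts A and FE.

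These definitions work whether the 50 mg step is per dose or per day, and they propose no clinical dosing rule.

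The cost is SAP wording and programming. Protocol 6.9.1 already requires reductions and interruptions to be recorded, and the SAP already uses the M3814 administration page and the action-taken field. The eCRF is not among the documents, so whether a reason is captured for each hold needs checking.
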